Thrombopoietin (TPO) is a protein made by the body that is important for normal production of platelets by the bone marrow. TPO may also be able to stimulate bone marrow stem cells to produce red cells and white cells. TPO cannot be given by mouth, and as an alternative, a drug, eltrombopag, has been designed that acts in the same way as TPO but is stable and active when given by mouth. Eltrombopag has been shown to safely increase platelet numbers in healthy volunteers and in patients with chronic immune thrombocytopenic purpura (ITP). It has been recently granted accelerated approval by FDA on November 20, 2008 for the treatment of patients with chronic immune thrombocytopenic purpura (ITP) who have had an insufficient response to standard therapies.

We have previously shown encouraging results when eltrombopag is used to treat patients with severe aplastic anemia, with some patients responding with increases in platelets, red cells and white cells. Given these encouraging early preliminary results in our clinical trial using eltrombopag in SAA, and low toxicity and ease of administration of this drug, we now propose a non-randomized pilot phase II study of eltrombopag in moderate aplastic anemia patients with clinically significant thrombocytopenia or anemia. Patients with MAA may not reach criteria for SAA, but none the less may be transfusion-dependent or have significant symptoms from cytopenias. We hypothesize that patients with MAA as compared to SAA may have a better chance of response, due to better residual marrow function in MAA patients compared to SAA.

Eligible patients can have treated or untreated MAA, as well as counts meeting criteria for MAA following a partial response to treatment with immunosuppression for SAA. We will also include patients with bone marrow failure and unilineage cytopenia. Treatment response for the platelet lineage is defined as platelet count increases to 20,000/uL above baseline at 16 to 20 weeks, or freedom from platelet transfusions for ≥ 8 weeks in transfusion-dependent patients. For patients with anemia (untransfused hemoglobin ≤ 8.5 g/dL), a treatment response will be an increase in Hb by ≥ 1.5 g/dl at four months, measured on at least 2 serial measurements and sustained for 1 month or more without transfusion support **OR** for transfusion dependent patients, reduction of units of RCC transfused by 50%/8 weeks compared with the pretreatment transfusion number in the previous 8 weeks or transfusion independence (no transfusions for ≥ 8 weeks). Subjects with evidence for a clinical response in any lineage at 16 weeks but not yet meeting full primary endpoint response criteria, and who are tolerating investigational treatment, may receive an additional 4 weeks of eltrombopag and be reassessed after 20 weeks. At that time, if they meet primary endpoint response criteria, they will be eligible to enter the extended access part of the study. If they do not meet primary endpoint response criteria, eltrombopag will be discontinued.

The **primary objective** is to assess the safety and efficacy of the oral thrombopoietin receptor agonist (TPO-R agonist) eltrombopag in moderate aplastic anemia patients or patients with bone marrow failure and unilineage cytopenia. **Secondary objectives** include the analysis of the incidence and severity of bleeding, clonal evolution to PNH, clonal chromosomal population in bone marrow, myelodysplasia by morphology, or acute leukemia and the impact on quality of life.

Table of Contents

1.0	OBJECTIVES	4
2.0	BACKGROUND AND SCIENTIFIC JUSTIFICATION	4
3.0	STUDY DESIGN.....	17
4.0	ELIGIBILITY ASSESSMENT.....	18
4.1	Inclusion criteria	18
4.2	Exclusion criteria	19
5.0	TREATMENT PLAN.....	20
6.0	CLINICAL MONITORING	23
7.0	ANCILLARY LABORATORY RESEARCH STUDIES	27
8.0	BIostatistical CONSIDERATIONS	28
8.1	Objectives	28
8.2	Endpoints	29
8.3	Sample Size.....	29
8.4	Statistical Methods.....	30
8.5	Stopping rules	30
8.6	Off Study Criteria	31
9	DATA AND SAFETY MONITORING	32
9.1	Data and Safety Monitoring.....	32
9.2	Event Characterization and Reporting	33

1.0 OBJECTIVES

The **primary objective** is to assess the safety and efficacy of the oral thrombopoietin receptor agonist (TPO-R agonist) eltrombopag in patients with moderate aplastic anemia or bone marrow failure with unilineage cytopenia.

Secondary objectives include the analysis of the incidence and severity of bleeding episodes, clonal evolution to PNH, clonal chromosomal population in bone marrow, myelodysplasia by morphology, or acute leukemia and the impact on quality of life.

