- Increases in hepatobiliary values (ALT, AST, bilirubin, alk phos) were seen in 16/164 subjects (9.7%) in the eltrombopag group (all doses), compared with 5/67 (7.5%) in the placebo group. These elevations in liver aminotransferase were generally asymptomatic and returned to baseline after discontinuation of therapy.
- One case of thromboembolism was observed (platelet count 108,000/uL) in the eltrombopag 50 mg treatment group in a subject who died from sepsis of pulmonary origin.
- Preclinical findings that indicated potential for phototoxicity, cataracts and renal tubular toxicity did not appear to translate to clinical consequences during short-term use.
- Transient decreases in platelet counts to levels below baseline were observed in both treatment groups after eltrombopag treatment ended. However, the decreases in platelet count were not accompanied by a clinically meaningful increase in bleeding symptoms.

TRA105325 (Extend) (chronic ITP Study): An open-label, dose-modification, Phase 3 extension study to evaluate the safety and efficacy of eltrombopag for the treatment of 302 subjects with ITP who were previously enrolled in an eltrombopag trial. Of the 302 subjects enrolled in the study, 186 (62%) achieved a platelet count ≥ 50 Gi/L in the absence of rescue therapy for $\geq 50\%$ of on-treatment assessments. Response rate in subjects with and without concomitant ITP medication used as baseline was 54% and 65%, respectively, and in subjects who were or were not splenectomised at baseline was 51% and 68%, respectively. The incidence of any bleeding symptoms (WHO grades 1-4) decreased from 57% at baseline to 16% at Week 52, 19% at Week 104, 12% at Week 156, and 14% at Week 208. Clinically significant bleeding (WHO grades 2-4) decreased from 17% at baseline to 4%, 5%, 0%, and 0% at Weeks 52, 104, 156, and 208, respectively.

TRA108057 (Repeat) (chronic ITP study): An ongoing, Phase II, multi-center, open label single group repeat dose study to evaluate the efficacy, safety and tolerability of repeated, short term administration of eltrombopag initially administered as 50 mg tablets once daily in subjects with previously treated chronic ITP (66 subjects with ongoing enrollment). In general, the results from the ongoing REPEAT and EXTEND studies confirmed the safety and efficacy profile noted in the completed TRA100773A and TRA100773B and are summarized below:

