Primary Endpoint by Baseline Disease Characteristics: Data presented in this section are pooled analyses of the TRA100773A and TRA100773B placebo and eltrombopag 50 mg treatment groups. Eltrombopag increased platelet counts after up to 6 weeks of dosing both for subjects who had baseline platelet counts of ≤ 15 K/uL and for those who had baseline platelet counts > 15 K/uL. A higher percentage of subjects in both treatment groups with baseline platelet counts > 15 K/uL achieved a platelet count ≥ 50 K/uL compared to subjects with a baseline platelet count ≤ 15 K/uL. No significant interaction between response and baseline platelet count status was observed ($p=0.443$). Analysis of responders at the Day 43 Visit demonstrated that eltrombopag increased platelet counts after up to 6 weeks of dosing for subjects who used ITP medication at randomization and for those who did not. No significant interaction between the response to treatment and the use of ITP medication at randomization was observed ($p=0.893$).

Analysis of responders at the Day 43 Visit demonstrated that eltrombopag increased platelet counts after up to 6 weeks of dosing for subjects regardless of splenectomy status. The percentage of subjects in the eltrombopag treatment group who achieved a platelet count ≥ 50 K/uL was similar regardless of splenectomy status. No significant interaction between response and splenectomy status was observed ($p=0.661$).

Analysis of Bleeding: Results of bleeding signs and symptoms reported via the World Health Organization (WHO) Bleeding Scale during the TRA100773A and TRA100773B are presented. The WHO Bleeding Scale has 5 grades: Grade 0 - no bleeding; Grade 1 - petechiae; Grade 2 - mild blood loss; Grade 3 - gross blood loss; and Grade 4 - debilitating blood loss. To analyze the data, subjects' assessments were summarized into categories: no bleeding (Grade 0), any bleeding (Grade 1 to Grade 4) and clinically significant bleeding (Grade 2 to Grade 4) (Table 2).

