3.0 STUDY DESIGN

[figure not shown]
The study is designed as a non-randomized, Phase II, dose modification study of the oral TPO-R agonist eltrombopag in moderate aplastic anemia patients or those with bone marrow failure with unilineage cytopenia. The primary endpoint is measured at 16 to 20 weeks (+/- 7 days). Subjects with evidence for a clinical response in any lineage at 16 weeks but not yet meeting full primary endpoint response criteria, and who are tolerating investigational treatment, may receive an additional 4 weeks of eltrombopag and be reassessed after 20 weeks (+/- 7 days). At that time, if they meet primary endpoint response criteria, they will be eligible to enter the extended access part of the study. If they do not meet primary endpoint response criteria, eltrombopag will be discontinued. Subjects who cannot tolerate the medication or fail to respond by 16 to 20 weeks (+/- 7 days) will go off study. Drug dose during extended access will be at the lowest dosage that maintains stable blood counts or taken off drug for robust response until they meet off study

criteria or the study is closed. If subjects are taken off drug for robust response during extended access and maintain response, they will be taken off study after 3years.

Protocol Schema prior to January 8, 2015:

Protocol Schema after January 8, 2015:

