8.2 Endpoints

The **primary endpoint** will be the portion of drug responders as defined by changes in the platelet count and/or platelet transfusion requirements or hemoglobin and/or PRBC transfusion requirements and the toxicity profile as measured using the CTCAE criteria. Treatment response for the platelet lineage is defined as an absolute increase of $\geq 20 \times 10^9/L$ above baseline at 16 or 20 weeks, measured on at least two serial measurements performed one week apart and sustained for 1 month or more without support of platelet transfusions, or for transfusion dependent patients stable platelet counts with transfusion independence for ≥ 8 weeks. For patients with anemia (untransfused hemoglobin ≤ 8.5 g/dL), a treatment response will be an increase in Hb by ≥ 1.5 g/dL at four months, measured on at least 2 serial measurements and sustained for 1 month or more without transfusion support **OR** for transfusion dependent patients, reduction of units of RCC transfused by 50%/8 weeks compared with the pretreatment transfusion number in the previous 8 weeks or transfusion independence (no transfusions for ≥ 8 weeks).

Criteria for response: Treatment response for the platelet lineage is defined as platelet count increases to 20,000/uL above baseline at 16 or 20 weeks, or freedom from platelet transfusions for ≥ 8 weeks in transfusion-dependent patients. For patients with anemia (untransfused hemoglobin ≤ 8.5 g/dL), a treatment response will be an increase in Hb by ≥ 1.5 g/dL at four months, measured on at least 2 serial measurements and sustained for 1 month or more without transfusion support **OR** for transfusion dependent patients, reduction of units of RCC transfused by 50%/8 weeks compared with the pretreatment transfusion number in the previous 8 weeks or transfusion independence (no transfusions for ≥ 8 weeks). We will analyze a composite of both lineage responses and the individual responses.

Secondary endpoints will include incidence of bleeding, changes in serum thrombopoietin level (as measured by enzyme-linked immunosorbent assay), clonal evolution to PNH, clonal chromosomal population in bone marrow, myelodysplasia by morphology, or acute leukemia and health related *General Quality of Life (FACT questionnaire)* for Subjects ages 18 and older will be completed at baseline and 16 weeks.

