8.4 Statistical Methods

The change of quality of life measure from baseline will be examined by the paired t-test or the Wilcoxon signed-rank. The planned analyses will include descriptive statistics on the proportions of responses (i.e. % subjects with treatment response) and the time to response. The response probabilities will be estimated using the sample proportions and their inferences including confidence intervals and hypothesis testing. Distributions of the sample proportions will be evaluated using Binomial distributions and their normal approximations.

The time to responses will be analyzed using appropriate tools in survival analysis, such as cumulative incidence estimate and Cox regression analysis for covariates, which takes consideration of both death without the event of interest as a complete risk and random censoring due to loss of follow-up. Graphical tools will be used to display the appropriate estimates (i.e. estimated proportions, the cumulative incidence curves, Kaplan-Meier curves) and their corresponding 95% confidence intervals. The Kaplan-Meier estimates and Cox regression will be used to evaluate the probability distributions of overall survival time.

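### Bleeding incidence and severity is a secondary objective, but the plan has no graded bleeding assessment, no severity endpoint and no bleeding analysis, so low-grade bleeding is likely undercounted and within-patient change cannot be reliably estimated

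*Combined protocol and SAP*

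**What the plan says.** The secondary objective is in section 1.0: "Secondary objectives include the analysis of the incidence and severity of bleeding episodes". Section 8.1 repeats it, and the synopsis says the same in nearly the same terms.

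Section 8.2 is narrower: "Secondary endpoints will include incidence of bleeding". It names no severity measure, scale, time window or comparison.

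Section 8.4 says "The planned analyses will include descriptive statistics on the proportions of responses" and goes on to time to response and overall survival. The only change from baseline it plans to test is quality of life: "The change of quality of life measure from baseline will be examined by the paired t-test or the Wilcoxon signed-rank". Bleeding is not mentioned.

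Sections 6.1 to 6.4 and Appendix B schedule history and examination, or a clinical assessment, at pre-study and at week 16/20, but no bleeding item or scale at any visit.

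Section 9.2.2 has all adverse events recorded and graded by CTC version 4.0. It also says that unscheduled laboratory results or patient reports that do not reach grade 3 or 4 go into the hospital record system and not into the study database.

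A bleeding scale appears only in the background on the ITP trials (2.4.6): "The WHO Bleeding Scale has 5 grades". There it is applied repeatedly and read against baseline: "The incidence of any bleeding symptoms (WHO grades 1-4) decreased from 57% at baseline to 16% at Week 52".

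**The concern.** Objective, endpoint, data collection and analysis should match, and for bleeding they do not. Severity is lost between 8.1 and 8.2, and both incidence and severity are lost between 8.2 and 8.4.

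This is more than missing detail that an analyst could supply later. A grade not recorded before the first dose can at best be reconstructed from notes. Section 3.0 describes a "non-randomized, Phase II, dose modification study" with no control group, so each subject's own baseline is the only internal comparator.

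Section 2.2 calls bleeding the major symptom of thrombocytopenia in aplastic anemia. It adds that more than half of the later deaths in patients who do not respond to immunosuppression are due to bleeding. An undercounted or ungraded result would leave little to report on an outcome that matters to these patients.

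**Working it through.** **Step 1. The bleeding objective followed through the plan.**

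| Place | Incidence | Severity | Baseline grade | Analysis |
|---|---|---|---|---|
| Synopsis, 1.0, 8.1 | yes | yes | not stated | promised |
| 8.2 | yes | no | no | no |
| 6.1 to 6.4, Appendix B | no item | no item | no item | not applicable |
| 8.4 | no | no | no | none |
| 9.2.2 | through adverse events | CTC v4.0 grade | general history and examination only | none |

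**Step 2. What the adverse-event route can and cannot supply.**
- It can supply reported bleeding on drug with a grade. The disease-related exclusion in 9.2.2 covers hematologic laboratory values and transfusion dependence, not bleeding.
- At weeks 2 to 14 and week 18, Appendix B schedules only blood counts, hepatic tests and some pregnancy tests. Bleeding in those weeks would often reach the team as a patient report or home progress note, and 6.2 requires those notes only if available. If such a report is unscheduled and below grade 3, 9.2.2 keeps it out of the study database.
- Events already listed in the label or brochure are reported only under set conditions, one being absence at the baseline examination. Ecchymosis is on the expected list for severe aplastic anemia (10.3.1). Mild bruising that persists from entry may therefore not be reported.
- From 30 days after the last dose, adverse-event reporting is limited to drug-related events (9.2.2), yet subjects stopped for robust response are followed for up to 3 years (6.3.1).
- An event log does not show that bleeding present at entry has resolved.

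The first four bear on undercounting, and the last on change within patients.

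**Step 3. Size, as an illustration only.** The plan states no rate, precision or power for bleeding, so there is no figure to reproduce. The number of evaluable subjects, 33, is from 8.3.

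*Precision of an incidence.* Exact (Clopper-Pearson) 95% intervals for assumed counts:
- 3/33: 1.9% to 24.3%
- 10/33: 15.6% to 48.7%
- 20/33: 42.1% to 77.1%

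*Power of a paired comparison, had a baseline grade been recorded.* Let b be the proportion bleeding at baseline and q the proportion on drug, with the two assumed independent within subject. Then P(improve) = b(1 − q) and P(worsen) = (1 − b)q. Power is for the exact two-sided McNemar test at 5%, n = 33, by full enumeration.

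| b to q | P(improve) | P(worsen) | Power | Origin of the rates |
|---|---|---|---|---|
| 57% to 16% | 0.57 × 0.84 = 0.479 | 0.43 × 0.16 = 0.069 | 0.914 | EXTEND, baseline to week 52 |
| 62% to 25% | 0.62 × 0.75 = 0.465 | 0.38 × 0.25 = 0.095 | 0.810 | TRA100773A, Day 43 (4 of 16 assessed) |
| 62% to 39% | 0.62 × 0.61 = 0.378 | 0.38 × 0.39 = 0.148 | 0.369 | TRA100773B, Day 43 |
| 30% to 15% | 0.30 × 0.85 = 0.255 | 0.70 × 0.15 = 0.105 | 0.205 | assumed lower rates |
| 20% to 10% | 0.20 × 0.90 = 0.180 | 0.80 × 0.10 = 0.080 | 0.112 | assumed lower rates |

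The 62% is the midpoint of the 61% to 63% that 2.4.6 gives for the two 50 mg groups. If the trial stops after the 18 subjects of stage 1, the first three powers fall to about 60%, 46% and 17%.

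**The case against.** The strongest reply is that the stated objective can largely be met already. It promises an analysis of incidence and severity, not of change. All adverse events are recorded with a CTC grade, so incidence by worst grade with an exact interval could be tabulated. History and examination take place at pre-study and at week 16/20, and one reporting condition in 9.2.2 refers to the baseline examination, so baseline is not ignored. The list in 8.4 is worded as what the analyses will include and need not be exhaustive.

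Much of this stands. A reader might infer that bleeding on drug is not recorded at all, or that the objective cannot be answered whatever the effect. The documents do not support either, because 9.2.2 provides graded reports. What the reply does not meet is the database rule for sub-grade-3 unscheduled reports, the absence of any named item or grade at baseline, and the loss of severity in 8.2.

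A second reply concerns the power figures. TRA100773B required platelets below 30,000/uL. This trial admits moderate aplastic anemia with platelets up to 70,000/mm³ (4.1.1), and 5.2 expects some patients to have normal or near-normal counts in one lineage, so baseline bleeding may be much less common. The 57% to 16% change is at week 52, not week 16/20. This stands, so the figures are illustrative only.

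Third, a before-and-after comparison is itself uncontrolled and cannot separate the drug from natural course or from the transfusions that 5.6 permits. This also stands, and limits the comparison to a descriptive role.

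Fourth, the document is a late amendment (01/02/2019), and 5.1 speaks of enrolment of sachet users in the past tense. If enrolment is over, which is an inference, baseline grades can only be abstracted from existing records.

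**Conclusion.** The point holds in a limited form. Severity is promised in 1.0 and 8.1 and missing from 8.2. No scheduled visit carries a graded bleeding assessment, and 8.4 has no bleeding analysis. Bleeding on drug rests on CTC-graded adverse-event reports, from which low-grade events are likely to be undercounted. Change within patients cannot be reliably estimated.

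The size of the undercount cannot be calculated from the documents. If a graded baseline existed, 33 subjects would give a paired test power of about 11% to 91%. That range depends on the assumed bleeding rates and on independence between baseline and later status, so only large changes would be detected with confidence.

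It would go too far to conclude that the single arm as such makes the objective unanswerable. The obstacle to estimating change is the missing graded baseline and comparison. A causal reading would lack a control even after the fix. The primary endpoint, sample size and stopping rules are not affected. The change is worth making because it is cheap.

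**What to change.** - **8.2:** restore severity. Define any bleeding (grades 1 to 4) and clinically significant bleeding (grades 2 to 4) on one named scale, with a stated time window. The 5-grade WHO scale described in 2.4.6 is one candidate.
- **6.1 to 6.3 and Appendix B:** record that scale at pre-study, at week 16/20 or at drug stop for those who discontinue early, and at the NIH extended-access visits.
- **9.2.2:** enter bleeding events of every grade in the study database, including those from unscheduled patient reports.
- **8.4:** report the proportions with any and with clinically significant bleeding by worst grade, with exact 95% confidence intervals. Add the paired week 16/20 minus baseline difference with a 95% confidence interval, labelled descriptive and uncontrolled. State whether each table draws on the scale or on CTC-graded events, since the two gradings differ.
- **Subjects already enrolled:** abstract the baseline grade from the pre-study history and examination where documented, and state how many are missing.

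The cost is one form line at existing visits and a little more data entry, with no added visit, procedure or patient. The main drawback is that baseline grades for earlier subjects may be incomplete.
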